7. The level of side effects will be assessed at the end of each session on a 0 (not at all) to 10 (highest degree) scale used by Ahn et al. (2019) (37), which includes the following symptoms: 1. Itching; 2. Burning; 3. Headache; 4. Fatigue; 5. Nervousness; 6. Dizziness; 7. Difficulty concentrating. The total score is the sum of the 7 items, varying from 0 to 70. Higher scores indicate higher levels of side effects.

8. Treatment emergent event review: after each RS-tDCS session and clinical assessment, subjects will be asked "Have you had any new symptoms, new medical conditions or been started on new medication/treatment since we last saw you?". This information will help research staff to judge about potential adverse events related to the trial. In addition, changes in treatment will help researchers to account for them in data analysis and the study's results interpretation.

4.1. **STUDY INTERVENTION**

The study intervention is tDCS treatments delivered by the Soterix Medical mini-CT device (https://soterixmedical.com/research/remote/mini-CT). The device is a nonsignificant risk (NSR) device study because it does not meet the definition of a significant risk device under §812.3 (m) of the investigational device exemptions (IDE) regulation (21 CFR §812)

(https://www.accessdata.fda.gov/scripts/cdrh/cfdocs/cfcfr/CFRSearch.cfm?fr=812.3).

The Soterix Medical mini-CT device for the RS-tDCS includes: (1) 1 x 1 mini-CT tDCS device; (2) SNAPstrap headgear, a "cap"-like placement for simple positioning and uniform electrode placement; (3) SNAPpads (individually-packaged pre-moistened sponge), and snap connectors (Figure 1) (39).

[figure not shown]

Figure 1. Remotely supervised (RS-tDCS) Equipment. (1) 1 x 1 mini-CT tDCS device; (2) SNAPstrap headgear: "cap"-like placement for simple positioning and uniform electrode placement; (2a) markers for guidance in placement; (2b) electrode polarity labeling with fixed wiring. (3) SNAPpad: (3a) individually-packaged pre-moistened sponge; perforated packaging for easy opening; (3b) snap connectors. (adapted from Pilloni, G., A. et al., Brain Stimul 15(3): 707-716, http://creativecommons.org/licenses/by-nc-nd/4.0/, DOI: 10.1016/j.brs.2022.04.014). The figure at the bottom simulates an RS-tDCS session.

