The tolerability and safety of home-based tDCS were assessed over 6,779 sessions from six clinical trials, with daily session, varying from 10 to 60 applications. The authors reported no serious adverse events, a similar proportion of tingling (68%), itching (41%), and warmth sensation (42%) between active and sham groups, and no participant discontinuation due to lack of tolerability (39). As described in "Study procedures," a tolerability test will be performed as part of the orientation session to verify if the subject can tolerate the electric current established in the protocol. Subjects will be informed that they can stop an RS-tDCS session anytime. During the RS-tDCS session, the stimulation will be stopped if the subject reports a sensation of pain rated as an intensity of 7 or above on a 1-10 scale (46). If the subject reports any event of critical concern related since the last RS-tDCS session, the next RS-tDCS session will not start until clear that the event is not stimulation-related. All devices function only after the inclusion of a unlock code for one-time use. The unlock codes for one-time use allow the device to function only once a day, just after the inclusion of the code, with the level of electric current and duration of the session determined by the protocol, both (electric current level and duration of the session) pre-programmed on the device before it is delivered to the subject.

Imminent risk of suicide, for the purposes of this study, refers to a subject who is currently 1) thinking about suicide; 2) preparing for suicide and/or having planned for suicide; and has 3) some intent to act on the suicide plan within the very near future (generally 48 hours).

This may differ for each case and therefore, clinical judgment along with timely consultation are needed for determination of imminence. Thus, to assess imminent risk of suicide, the following procedures will be undertaken:

a) at the baseline assessment in the hospital:

- after the C-SSRS assessment, research staff will ask the subject if there is current active suicidal ideation with plan and intent. If the subject reports current active suicidal ideation plan and intent at the baseline, research staff will inform the subject that they need to communicate this information (about the active suicidal ideation with specific plan and intent) to the unit staff in charge of the patient due to safety concerns.

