17. DATA ANALYSIS PLAN

To assess feasibility, the primary outcome of this study, we chose a sample size of 20. To infer feasibility, at least 50% of the sessions should be performed successfully per subject for at least 70% of the subjects. This criterion is based on a study that reported dropout rates between 22% and 25% of home-based tDCS for patients with bipolar depression (40) and that therapeutic effects with tDCS could be achieved within one week of treatment (24). For each time point established, we will compare groups with a t-test or chi-square test, for continuous and categorical data, respectively (a p value<0.05 will be considered significant).

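### The side-effects questionnaire is scored only as a 0-70 sum of seven unlike symptoms, so a marked effect on one local symptom is diluted; an item-level descriptive table should be added (minor)

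*Combined protocol and SAP*

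**What the plan says.** Section 4, secondary outcome 7, sets the scale and timing: "The level of side effects will be assessed at the end of each session on a 0 (not at all) to 10 (highest degree) scale". The symptoms are "1. Itching; 2. Burning; 3. Headache; 4. Fatigue; 5. Nervousness; 6. Dizziness; 7. Difficulty concentrating". The only score defined is the total: "The total score is the sum of the 7 items, varying from 0 to 70". No proportion by symptom, worst rating or severity category is defined for this questionnaire anywhere in the document.

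Section 17 does not name side effects. It gives one general rule, "For each time point established, we will compare groups with a t-test or chi-square test, for continuous and categorical data, respectively", with the criterion that "a p value<0.05 will be considered significant". It does not say how up to ten sessions per subject are to be combined.

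Safety is also covered elsewhere:

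- Section 16 compares the arms on each adverse event (at least one occurrence, Fisher's exact test), describes the numbers of individual events, and records intensity and causality for all adverse events.
- Secondary outcome 8 asks about new symptoms after each session and each clinical assessment.
- Section 8, under the stimulation sessions, lists the side-effects questionnaire and the adverse-event review as separate steps.
- Section 9 has a rule for stopping stimulation that rests on a single pain rating.

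The cited tolerability evidence (Sections 2, 4.1 and 9) is given by symptom: "a similar proportion of tingling (68%), itching (41%), and warmth sensation (42%) between active and sham groups".

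**The concern.** The seven items do not measure one thing. Itching and burning are sensations at the electrode site. Fatigue, nervousness and difficulty concentrating correspond closely to the lassitude, inner tension and concentration items of the MADRS, which this trial collects as an outcome in its own right (secondary outcome 6). Residual depression therefore adds to the side-effect total whatever the stimulation does. If active treatment relieved those symptoms, the relief could offset a local effect within the same score.

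At stake is what this pilot can say about tolerability. It could collect item ratings at up to 20 x 10 = 200 sessions, that is 1,400 individual ratings, and report only a total. A concentrated excess of one local symptom on active stimulation would then appear as a small shift in that total, and a small shift is easily read as good tolerability. A full trial planned from this pilot would have no figures by symptom from the questionnaire.

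**Working it through.** **Inputs from the document.** Seven items, each 0 to 10 (Section 4, outcome 7). Total sample 20 ("To assess feasibility, the primary outcome of this study, we chose a sample size of 20", Section 17), randomized 1:1 (Section 4.1), so about 10 per arm. Significance level 0.05; sidedness is not stated and two-sided is assumed.

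**The plan's own figure.** 7 x 0 = 0 and 7 x 10 = 70. The stated range reproduces.

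**Ranking of individual subjects** (no assumptions needed).

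- Burning 10, all else 0: total 10, and 10/70 = 14% of the range.
- A rating of 2 on all seven items: 7 x 2 = 14, and 14/70 = 20% of the range.
- Burning 7, all else 0: total 7, the same as a rating of 1 on every item.

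The sum ranks a maximal single local effect below mild ratings across the board.

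**Effect on the arm mean.** If 2 of 10 active subjects have an 8-point rise in burning, the mean total rises by 2 x 8 / 10 = 1.6 points, or 1.6/70 = 2.3% of the range.

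**Dilution when the whole arm shifts on one item.** The document gives no SDs or correlations, so these are assumed: item SD 1.5 to 2, common between-item correlation r from 0 to 0.6, one time point. The SD of the sum is SD_item x sqrt(7 + 42r).

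- SD 1.5: 1.5 x sqrt(7) = 3.97 at r = 0; 1.5 x sqrt(32.2) = 8.51 at r = 0.6.
- SD 2: 5.29 at r = 0; 11.35 at r = 0.6.

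Standardized differences and two-sample t-test power (noncentral t, 10 per arm):

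| Shift on one item | Item: difference / SD | Item: power | Sum: difference / SD | Sum: power |
|---|---|---|---|---|
| 2 points | 1.0 to 1.33 | 56-80% | 0.18 to 0.50 | 7-19% |
| 3 points | 1.5 to 2.0 | 89-99% | 0.26 to 0.76 | 9-36% |

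With 10 per arm, a t-test reaches 80% power only for a difference of about 1.32 SD.

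**Severe effect in a minority.** Simulation, 3,000 runs per setting, 10 per arm. Assumptions: independent items with background mean 1/SD 1 or mean 2/SD 2, rounded and limited to 0-10; burning set to 8 in a given share of active subjects.

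| Share affected | t-test on sum | t-test on burning | Fisher, burning 7 or above |
|---|---|---|---|
| 30% | 12-24% | 30-38% | 14-15% |
| 50% | 24-55% | 64-79% | 58-62% |

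With 10% or 20% affected, no method exceeds about 18%. With 0/10 in sham, Fisher's test needs 5/10 in active for p < 0.05 (p = 0.033; 4/10 gives p = 0.087).

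**Precision of item-level proportions.** Exact 95% intervals: 4/10 gives 12-74%; 8/20 gives 19-64%.

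The sum does dilute a single-symptom effect. Testing by item at this sample size detects only gross differences, so the gain from item-level reporting is in what becomes visible, not in power.

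**The case against.** The strongest reply is that the questionnaire is not the trial's safety analysis. Section 16 compares arms event by event and records intensity, staff ask about new symptoms after every session, and a single pain rating can stop stimulation. A reader might infer from outcome 7 that a severe burn would be averaged away altogether. The document does not support that: a burn recorded as an adverse event would be counted under Section 16. What remains is narrower. No section says when, or whether, a questionnaire rating is recorded as an adverse event. The two are collected as separate steps, and the question in outcome 8 concerns new symptoms since the last contact, so a sensation recurring at each session need not be captured there.

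A reader might also infer that the sum is what prevents comparison with the cited rates. It is not. The denominator of those rates is not stated and may be subjects or sessions, and the difference is large: if 41% were a per-session rate, the proportion of subjects with itching in at least one of ten sessions would be 41% under perfect within-subject correlation and 1 - 0.59^10 = 99% under independence. An itching proportion can be derived from the items as collected. Tingling and warmth are not on the questionnaire, so abandoning the sum would not supply them.

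Three further points stand. The t-test on the sum is inferred from a general sentence. The power contrast models a shift across the whole arm rather than one severe case. And the plan is silent on item-level reporting; it does not rule it out. The cited evidence also reports similar rates in the two arms and does not mention burning, so an excess on active stimulation is a possibility and not an expectation.

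**Conclusion.** The point holds as a minor one. The questionnaire has one planned score; that score mixes local sensations with symptoms of the underlying disorder and can rank burning 10 alone (10/70) below a rating of 2 throughout (14/70). No item-level summary is planned, and no link to the adverse-event analysis is stated. The ranking and the 1.6-point shift are plain arithmetic. The power figures depend on assumed SDs, correlations and background scores; they show the direction and rough size of the dilution and do not argue for seven tests.

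Severity is limited because this is one of eight secondary outcomes in a 20-subject feasibility trial, the primary outcome is session completion, and a separate adverse-event analysis exists.

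**What to change.** In outcome 7 and Section 17, add a descriptive table with one row per symptom, by arm, giving:

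- the proportion of subjects with any rating above 0, with an exact 95% confidence interval;
- the proportion of sessions with a rating above 0;
- the distribution of each subject's highest rating over the sessions completed.

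Make no significance tests on these rows. Give both proportions because the denominator of the cited rates is unknown. Sessions within a subject are not independent, so a simple binomial interval on the session proportion would be too narrow; show that proportion with its counts, or with an interval that allows for clustering by subject. Show the number of sessions completed per arm beside the table, since more sessions give more chances for a rating above 0.

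Keep the 0-70 sum as a secondary summary and say how sessions are combined for it. Add a sentence to Section 16 stating how item ratings relate to the recording and analysis of adverse events; the content of that rule is for the investigators. Note in the text that tingling and warmth are not collected, so only itching can be set beside the cited figures.

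The cost is a few sentences and one table from data already collected. The downside is seven rows in place of one score, with wide intervals at about 10 per arm.

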8. STUDY PROCEDURES

The pre-screening will be carried out through the electronic hospital medical record to identify potential subjects. Once the potential subject is identified, research staff will visit the unit where the patient is receiving treatment (inpatient unit or CPEP) and talk with unit staff in person, providing information about the study. Then, the research staff will ask unit staff to determine the most appropriate time for the research staff to meet with the patient based on knowledge of patient status and needs.

[figure not shown]
After screening and signing consent, the research study staff will collect demographic and general medical history data, apply the clinical questionnaires, and conduct the orientation tDCS session as part of the in-person baseline assessment (Table 1 and Figure 3). This demographic, general medical history, and clinical data will be collected and stored in the REDCap through a tablet or another portable electronic device. Per subject need/request, research study staff reads aloud instructions and questions while subjects hold the tablet to record their answers. If the REDCap site is down or malfunctioning, screening, consent, and questionnaires are completed on paper and later entered into REDCap.

The orientation session includes presenting the Soterix Medical mini-CT device to the subject to show how to turn it on/off, how to insert the device unlock codes for one-time use, how to correctly adjust the SNAPstrap headgear, and answer any questions they may have. As part of the orientation session, research staff will also conduct a 90-s tolerability test, with 2.0 mA as the starting point (electrical current intensity of the study protocol). During this test, the current intensity is ramped up to 2.0 mA and the subject will receive the stimulation for 90 seconds. The tolerability will be determined by subject rating below 7 on the 0-10 Visual Analogue Scale (VAS) of pain. If the subject finds the target tDCS dose intolerable (i.e., VAS 7 or higher), subjects will have the option of another test, with the amperage dose decreased by 0.5 mA (i.e., to 1.5 mA). If this lower amperage is also intolerable, the subject will be excluded from the study (39, 46). Thus, the orientation session aims to 1) familiarize the subject with the

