device, how to turn it on/off, and insert the unlock codes for one-time use; 2) to assess if the subject tolerates the protocol electric current through the tolerability test; 3) answer any questions the subjects may have. As the Soterix Medical mini-CT device will be with the subjects during the RS-tDCS sessions, subjects will be asked to sign an IRB-approved device loan agreement at the baseline.

Clinical questionnaires will be re-administered at day 14 [+ 7 days], day 30 [+ 7 days], and day 60 [+ 10 days] from the first RS-tDCS session session15 (Figure 3). While we aim to reach subjects on the phone for follow-up, research staff may email or text subjects to schedule the RS-tDCS sessions and clinical assessments. Subject identifying information and protected health information (PHI) is not exchanged in the text messages themselves. Detailed information about text messaging is included under the "Privacy and Confidentiality of Subjects and Research Data" section. Security risks associated with text messaging are described in detail during consent.

After baseline assessment, research staff not involved in the RS-tDCS supervisions and clinical assessments will randomize the subject to active or sham control group and set up the device condition (active or sham), program the intensity for the active condition (either 2.0 mA or 1.5 mA, according to the tolerability test) and duration (30 minutes) of each session, and get the device unlock codes for one-time use to be provided by the research staff to the subject immediately before each session. The discharge day will be tracked daily by the research staff through the electronic hospital medical record. Once the subject is discharged, research staff will deliver the RS-tDCS device by mail to the subject's address in a pre-paid FedEx package to send it back and contact the subject once the device has arrived at their home (by using the mail tracking number) to schedule the first RS-tDCS session.

*device set up for the condition (active or sham), and locked (unlock codes for one-time use will be provided before each session); **day 1 being the first RS-tDCS session and no sessions on weekends. CPEP: Comprehensive Psychiatric Emergency Program; DLPFC: dorsolateral prefrontal cortex; RS-tDCS: remotely supervised transcranial direct current stimulation.

RS-tDCS sessions:

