Research staff with training in using home-based tDCS by the Soterix Medical will meet with the subject via HIPAA-compliant videoconference previously scheduled. Subjects will be encouraged to find a distraction-free setting to complete treatment sessions. After guiding the subject with the proper adjustment of the SNAPstrap headgear and turning on the 1 x 1 Mini-CT device, research staff will provide the device unlock codes for one-time use to the subject. All ten device unlock codes for one-time use (one for each tDCS session) are obtained previously, just after the device is programmed to active or sham. The device unlock codes for one-time use allow the device to function only once a day, just after the inclusion of the code, with the level of electric current and duration of the session determined by the protocol, both (electric current level and duration of the session) pre-programmed on the device before it is delivered to the subject. Thus, the subject cannot alter the electric current level, the duration of the session, or use the device more than once a day. After each RS-tDCS session, research staff will apply the side effects questionnaire, review the subject's current treatment ("treatment review"), ask about any new or updated mental or physical symptoms since the last assessment (adverse events review), and apply the C-SSRS - screening version (C-SSRS SV) as part of the risk assessment (please, see more details on item "9. RISK TO SUBJECTS"). After the last RS-tDCS session (the tenth session), research staff will apply the feasibility questionnaire and blinding assessment. (Table 1). To assess blinding, the subjects will be asked the following question, "What treatment do you believe you have received??"(47). There will be three possible answers: 1) "active-tDCS"; 2)

"sham-tDCS" or 3) "Don't know". If the answer is "Don't know", research staff will ask "Would you be willing to provide your best guess about the treatment you received?", and could choose from two possible replies: 1) active-tDCS; 2) sham-tDCS (47, 48). We will use the Bang Blinding Index, which varies from -1 to +1, being 1 complete lack of blinding, +1 the opposite guessing, and 0 being related to perfect blinding (48). After the tenth session, the subject will be asked to send back the equipment in the pre-paid mail package to send it back.

Clinical assessments:

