16. DATA AND SAFETY MONITORING PLAN

Risk to study subjects is minimized by only employing well-trained and clinically experienced personnel. Routine hospital protocols are already in place for handling in-person and over-the-phone crises.

Adverse Events (AEs) and Serious Adverse Events (SAEs)

An adverse event is "any untoward or unfavorable medical occurrence in a human subject...temporally associated with the subject's participation in the research, whether or not considered related to the subject's participation in the research." A serious adverse event (SAE) is an event where a relationship to the research study cannot be ruled out, and the event is life-threatening/results in death OR disabling/incapacitating OR requires or prolongs hospitalization OR involves an overdose OR was otherwise unanticipated, related to the study procedures. Due to the nature of this study, suicide attempts and psychiatric hospitalizations are possible to

happen during its course. These events are considered SAEs and reported as such. In most circumstances, suicide attempts and psychiatric hospitalizations are expected for this population and, as a result, non-study related. As such, these SAEs will be reported at continuing review but only unexpected reported immediately to the IRB. Suicide deaths are reported to the IRB within 48 hours of learning of the death. In addition, the report includes investigators' judgment as to whether a relationship to the research study can/cannot be ruled out.

For all AEs, the date and time of onset and outcome, course, intensity, action is taken, and causality to study treatment will be assessed. Based on the review of the circumstances and as-needed consultation with co-investigators, the PI can reclassify an AE as an SAE. If considered related to the study, unanticipated adverse events involving risks to subjects or others will be reported by the PI to IRB. For each adverse event, the treatment groups are compared in a pair-wise fashion regarding the occurrence of at least one event using Fisher's exact tests; the numbers of individual events will also be described. All subjects are included in these analyses.

Confidentiality

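### The by-arm adverse-event comparison has no onset cut-off, so events between the in-hospital baseline and the first randomized session can enter it and dilute a true difference

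*Combined protocol and SAP*

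**What the plan says.** **When the question is asked.** Section 4, secondary outcome 8, states that "after each RS-tDCS session and clinical assessment, subjects will be asked" the following: "Have you had any new symptoms, new medical conditions or been started on new medication/treatment since we last saw you". Table 1 places this review at sessions 1 to 10 and at the day 14, 30 and 60 assessments, but not at baseline. Section 8 describes the same task: after each session staff are to "ask about any new or updated mental or physical symptoms since the last assessment (adverse events review".

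**What lies between baseline and session 1.** Baseline is done in person in the hospital and includes the tolerability test: "During this test, the current intensity is ramped up to 2.0 mA and the subject will receive the stimulation for 90 seconds". Randomization follows baseline. Then: "Once the subject is discharged, research staff will deliver the RS-tDCS device by mail". Staff contact the subject once the device has arrived, to schedule the first session. The length of this interval is not stated.

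**How events are compared.** Section 16 defines an adverse event by its timing relative to participation in the research. For each adverse event, "the treatment groups are compared in a pair-wise fashion regarding the occurrence of at least one event using" Fisher's exact tests, with all subjects included. For all adverse events, "the date and time of onset and outcome, course, intensity, action is taken, and causality to study treatment will be assessed". Neither Section 16 nor Section 17 says that onset must follow the first randomized session.

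**The concern.** An event that begins in the ward, at discharge or while the device is in the mail cannot have been caused by the randomized stimulation. The first review nevertheless collects it, and the Section 16 rule, followed as written, counts it for the arm to which the subject was assigned. A subject who already has that event counted contributes nothing to the contrast if the same event recurs on treatment, because the indicator is already yes.

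The interval is not likely to be quiet. Section 2 cites a review in which about 20% of suicides and attempts fell within 15 days of discharge, and Section 16 classes suicide attempts and psychiatric hospitalizations as serious adverse events. (The 20% is a share of events, not a risk per subject, so it cannot be used as b.) At stake is a safety comparison that becomes more likely to miss a real excess in the active arm, in a pilot meant to inform a full trial.

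**Working it through.** The plan states no adverse-event rate, event count or power, so it has no figure to reproduce. Section 17 gives the sample size of 20 as a choice.

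**Step 1: the look-back window.** The review is not scheduled at baseline or just before session 1. The first one is after session 1, and the last scheduled assessment before it is the in-hospital baseline. Nothing resets the window at the start of stimulation.

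**Step 2: the counting rule.** The adverse-event definition starts with participation, the indicator is any occurrence, and the analysis set is everyone. Events from Step 1 that are judged to be adverse events therefore qualify.

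**Step 3: effect on the risk difference.** Let b be the share of subjects with a given event between baseline and session 1, equal in both arms because no randomized stimulation has been given, and let p be the on-treatment risk. Assuming independence:

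- observed risk = 1 − (1 − b)(1 − p)
- observed difference = (1 − b)(p_active − p_sham)

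For example, at b = 30% with 40% active and 10% sham: 1 − 0.7 × 0.6 = 0.58 and 1 − 0.7 × 0.9 = 0.37, a difference of 0.21 = 0.7 × 0.30.

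**Step 4: effect on the test.** Inputs are 20 subjects (Section 4) allocated 1:1 (Section 4.1), hence about 10 per arm. The 0.05 level is stated in Section 17 for the time-point tests; its use for Fisher's test, and a two-sided test, are assumptions. Power is exact, by enumerating both binomial distributions. The values of b and p are assumed.

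| b | 40% vs 10%: observed active, sham | Difference (points) | Fisher power | 60% vs 10%: difference (points) | Fisher power |
|---|---|---|---|---|---|
| 0% | 40%, 10% | 30 | 15% | 50 | 47% |
| 10% | 46%, 19% | 27 | 11% | 45 | 34% |
| 20% | 52%, 28% | 24 | 8% | 40 | 24% |
| 30% | 58%, 37% | 21 | 6% | 35 | 18% |
| 40% | 64%, 46% | 18 | 5% | 30 | 13% |

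The row b = 0 is what an onset cut-off would restore.

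**Step 5: false differences.** With equal on-treatment risks (10% or 30% in both arms) and b from 0 to 40%, the chance of p < 0.05 stays at or below 1.3%. Earlier events therefore do not produce spurious findings.

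**Step 6: how little the test can detect.** With 10 per arm and no events in one arm, the other needs at least 5 (p = 0.033).

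**The case against.** The strongest reply is that the plan is not wrong as it stands. Section 16 compares adverse events, not treatment-emergent events. The latter term names only an interview item whose answers help staff judge whether an adverse event has occurred. Since randomization follows baseline, counting events from about that point is a legitimate randomized comparison. Onset and causality are recorded, so the split can be made at any time. Acute effects such as itching, burning and headache have their own score at the end of each session, with no look-back. The comparison is also made event by event, so dilution needs the same type of event before session 1. And the test has little power either way.

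Most of this stands, and it limits the size of the point. It does not remove it: recorded onset helps only if a rule uses it, and the written rule does not.

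Three stronger readings are tempting and not supported:

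- *A reader might infer that the tolerability test makes sham look as if it causes stimulation effects.* Sham sessions deliver real current themselves. Section 4.1 describes a 30-second ramp up to 2 mA and a 30-second ramp down, at the beginning and end, which is 2 × (30 + 30) = 120 seconds per session. One 90-second test adds little to that. Sensations while staff are present fall outside the look-back, and those who cannot tolerate the test are excluded.
- *A reader might infer bias toward one arm.* Steps 3 and 5 show dilution only.
- *A reader might infer that treatment changes before session 1 should be dropped as well.* The clinical scales take their baseline in hospital, so a drug started at discharge is a real change relative to that baseline.

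**Conclusion.** The point holds as a missing analysis rule, not as missing data. As written, events between the in-hospital baseline and the first randomized session can enter the by-arm Fisher comparison and reduce a true risk difference by the factor (1 − b). In the assumed 40% versus 10% example, the 30-point difference becomes 27 points at b = 10% and 21 at b = 30%.

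This rests on b being equal in the two arms on average and independent of later events, and on assumed risks. The documents give neither the length of the interval nor any event rate, so the actual loss is unknown and could be small. The feasibility outcome and the per-session side-effects score are untouched. The change is worth making because the better rule is nearly free, not because it would rescue a test that has 15% power in that example even without dilution.

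**What to change.** In Section 16, restrict the by-arm adverse-event comparison to events with onset, or worsening of an existing condition, at or after the start of the subject's first RS-tDCS session, using the onset date and time already collected. List events between baseline and that point separately by arm, marking any that followed the tolerability test, so that nothing is lost from safety reporting.

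For treatment changes, keep everything since baseline in the tabulation and flag each as before or after session 1.

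The cost is one or two sentences in the plan and one derived variable; no new data are needed. The downside is slightly fewer events in the comparison. Because power remains low, proportions by arm and the listing of earlier events will tell the reader more than the p values.
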